## ***VIII. Risks and Benefits***

The only foreseeable risks of this study are loss of confidentiality, boredom or fatigue from filling daily surveys.

There are no direct benefits to subjects.

After completion of the proposed RCT, we expect to see a decrease in opioid consumption patterns after shoulder arthroplasty, as well as an increase in disposal of unused opioid pills. One of our expected outcomes is that our educational interventions will have a positive influence on opioid consumption after surgery. In addition, we expect that this group will be encouraged to use drug-free pain management techniques and find the educational materials satisfactory. Our second expected outcome is that the proposed disposal method will have high satisfaction rate for patients to dispose of unused opioid pills. The implementation of a secure and efficient disposal mechanism will encourage patients to remove potentially dangerous medications from their homes and this disposal program could become a standard of care practice for shoulder arthroplasty procedures. To date, there is no standardized educational intervention that is routinely administered preoperatively to all patients to approach postoperative opioid consumption, disposal, and pain management techniques. This proposal aims to gather the necessary information to build a larger study and eventually include other surgical procedures.

## ***IX. Data Analysis Plan***

The primary outcome measure is opioid consumption with and without pre-operative opioid education. By comparing the two arms we will determine the difference in opioid consumption between groups of patients who receive education and those who do not. We will also analyze opioid disposal in the two groups and compare disposal rates.

Descriptive statistics (means, medians, percentages, standard deviations, and interquartile ranges) for all variables will be computed overall and for each intervention group. The distributions of continuous variables will be evaluated for normality. If distributions are non-normal, continuous variables will be described as median (interquartile range) and compared across intervention groups using Wilcoxon-rank sum tests. Otherwise, continuous variables will be described as mean $\pm$ standard deviation and compared between intervention groups using independent t-tests. Categorical variables will be reported as frequencies(percentages) and compared between groups using the chi-square or exact test, as appropriate. To account for multiple comparisons between the three groups, p-values will be adjusted using the stepdown Bonferroni approach. We will utilize the chi-square test to determine whether there is a significantly greater proportion who (Hypothesis 1) return more than 10 tablets in Arm 2 versus Arm 1; and (Hypothesis 2) properly dispose of unused tablets in Arm 2 versus control Arm 1. If necessary, we will adjust for potential covariates using logistic regression in place of the chi-square test with the control group serving as the referent group.

A sample size estimate was performed based on previous literature and data from our pilot study that showed nearly 55% of subjects returned 10 or more out of 40 tablets.

Assuming ~55% will return 10 or more out of 40 tablets in the control group, a total of 68 subjects per group (n=136 total, with calculated 10% drop out) would provide 80% power, with an alpha level of 0.05 (2-sided test), to detect a 25% difference in the proportion who return 10 or more tabs in the brochure/video intervention group (35%).

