### **III. Study Aims**

AIM 1: Develop pre-operative opioid educational modules for patients undergoing shoulder arthroplasty.

AIM 2: Evaluate the impact of educational materials on opioid consumption following shoulder arthroplasty when compared to standard of care. Hypothesis: Pre-operative educational modules, developed by an interdisciplinary team, will prove to be successful in decreasing the amount opioid medication taken after shoulder arthroplasty.

AIM 3: Evaluate a structured and streamlined disposal protocol and its effect on opioid disposal rates. Hypothesis: By promoting and implementing a structured and secured opioid disposal mechanism, patients undergoing shoulder arthroplasty will more frequently dispose of excess opioid medications.

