During their preoperative work-up visit, at IRL and Main Hospital, patients will be invited to participate in the research study. The research coordinator will discuss the study with potential subjects in a private office or exam room. If the patient shows interest in participating, the research coordinator and the patient will go through the process of consent of participants. Potential subjects will be explained that the purpose of the study is to assess opioid consumption and disposal after shoulder replacement surgery, and that after their surgery, they will have to answer daily questionnaires about pain management and opioid consumption, that will be delivered through text message only during the first 2 weeks after surgery. Adequate time will be allotted to the patients in clinic to consider participating in the study. The study will require a waiver of an element of consent, in relation to the use of deception and blinding of subjects. Without the waiver of the element of consent our study results may be biased as subjects in the standard of care group may potentially change their behavior if they were aware of the information being concealed.

Patients will be screened according to inclusion and exclusion criteria at their indication visit for total shoulder arthroplasty. Participants will receive daily text messages with a link to a REDCap survey during the 2 weeks following the surgery. For participants who did not answer the daily surveys, or for the ones who are still taking opioid medications after 2 weeks, a survey will be available at clinic. Subjects will be able to answer the survey at their scheduled postoperative visits (standard of care). Participants will not have to attend any visits for research purposes only.

Patients will be randomized utilizing redcap. The randomization scheme will be performed in a 1:1 ratio.

After signing the informed consent, participants will be randomized into one of the 2 study arms (Arm 1: control/SOC, Arm 2: education and disposal).

Participants in Arm 1 will be the control group. These patients will undergo evaluation and treatment for total shoulder arthroplasty according to the current standard of care at the institution. This does not currently include any preoperative educational material regarding opioid consumption and/or disposal.

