Participants in Arm 2 will receive at their preoperative work-up visit a brochure and will watch an educational video. Both educational materials (brochure and video) will address information about opioid medication, pain management techniques and how to properly dispose of any excess opioid medication after the surgery. In addition, participants in Arm 2 will receive an envelope in which they will be able to dispose their unused opioid pills. These envelopes will be the same ones used in our pilot study (IRB# 202012142). The disposal method consists of secured, labeled envelopes to dispose of the excess of Opioid medication. These envelopes will be provided by “Sharps Compliance, Inc.”, a company that manages pharmaceutical waste disposal programs for healthcare facilities. Through their “TakeAway Medication Recovery System Envelope (USPS)” they allow the collection and disposal of controlled substances (Schedules II-IV) and non-controlled medications. Subjects will be explained how to use the envelope and that since it is labeled they will not have to cover any charges.

Potential subjects will be explained that the purpose of the study is to assess opioid consumption and disposal after shoulder replacement surgery, and that after their surgery, they will have to answer daily questionnaires about pain management and opioid consumption, that will be delivered through text message only during the first 2 weeks after surgery. The questionnaires will be built using REDCap platform. Text messages will be sent using a platform built by the Mobile Technology Lab at UIHC.

Participants who did not answer the daily survey, or who continue taking opioid medications after 2 weeks following surgery, will have the opportunity to answer the survey at their postoperative visit at the Shoulder Clinic, using the clinic's tablets, either at their 2-week or 6-week postoperative visit.

Subjects lost to follow up will not be recontacted.  
Subjects will not receive monetary compensation.

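### The two-arm contrast measures the education-plus-disposal package, but Aim 2, the primary outcome statement and Aim 3 credit its effects to single components

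*Combined protocol and SAP*

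**What the plan says.** **The arms (VI. Study Procedures).** There are two: "Arm 1: control/SOC, Arm 2: education and disposal". On allocation: "The randomization scheme will be performed in a 1:1 ratio". On education: "Participants in Arm 2 will receive at their preoperative work-up visit a brochure and will watch an educational video". Both materials cover, among other things, "how to properly dispose of any excess opioid medication after the surgery". On top of this, "participants in Arm 2 will receive an envelope in which they will be able to dispose their unused opioid pills". Arm 1 is the institution's usual care, which VI says contains no preoperative teaching on opioid use or disposal. No study envelope is described for Arm 1.

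**Wording that credits one component.**
- Aim 2 (III, repeated in V): "Evaluate the impact of educational materials on opioid consumption following shoulder arthroplasty when compared to standard of care". Its hypothesis expects the educational modules to reduce the amount of opioid taken.
- Aim 3 (III, repeated in V): "Evaluate a structured and streamlined disposal protocol and its effect on opioid disposal rates". Its hypothesis expects the disposal mechanism to make disposal more frequent.
- IX, first paragraph: the primary outcome is consumption with and without education, and comparing the arms is to give "the difference in opioid consumption between groups of patients who receive education and those who do not".
- V and IX, sample size text: the intervention group is named by its brochure and video, without the envelope.
- VIII, first expected outcome: the educational interventions are expected to influence consumption.
- Abstract, objectives 2 and 3: the educational intervention and the disposal mechanism are listed as separate effects to study.

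**Wording that describes the package.** The Abstract's comparison and hypothesis, the closing paragraph of the Background narrative, the arm label in VI, and Hypotheses 1 and 2 in IX, both of which compare Arm 2 with Arm 1.

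**The concern.** A difference between the arms could arise from the teaching, from the envelope, or from the two acting together. If the aims and the first paragraph of IX are followed literally, a positive trial would be reported as showing that education lowers consumption and that the disposal mechanism raises disposal. Neither statement follows from the comparison. This matters for use of the result: VIII suggests that the disposal program could become standard practice and that the work will inform a larger study and other procedures. A service that adopted only one part could not rely on this trial for the effect of that part.

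**Working it through.** **1. What is randomized.** Classify patients by education (no/yes) and envelope (no/yes). Of the four possible cells, the plan fills two:

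| | No envelope | Envelope |
|---|---|---|
| No education | Arm 1 | none |
| Education | none | Arm 2 |

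**2. What the contrast estimates.** For either outcome, let *e* be the effect of education alone, *v* the effect of the envelope alone, and *i* their interaction. Then

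Arm 2 − Arm 1 = *e* + *v* + *i*.

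This is one equation in three unknowns. More patients estimate the sum more precisely but do not divide it. The logistic regression allowed in IX does not help either: by assignment, the education and envelope indicators are identical for every patient, so a model cannot hold one fixed and vary the other. No factorial structure, component arm or mediation analysis is planned. IX mentions three groups, but VI randomizes only two.

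**3. Why no share can be quoted.** Take the 25-point difference in the sample size text, by size only. It fits *e* = 25, *v* = 0, *i* = 0. It fits equally *e* = 0, *v* = 25, *i* = 0, or *e* = 0, *v* = 0, *i* = 25. It also fits *e* = −25, *v* = 50, *i* = 0, since −25 + 50 = 25. A component's share can therefore be negative or above 100%. These are illustrations, not estimates.

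**4. The tablets-returned outcome.** Hypothesis 1 and the sample size use tablets returned, not tablets taken. For a patient given 40 tablets,

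returned = 40 − taken − kept.

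Suppose two patients each take 20, leaving 40 − 20 = 20. The one who mails all 20 has returned 20; the one who keeps all 20 has returned 0. Consumption is 20 in both. An envelope given only to Arm 2 could therefore raise returns with no change in intake. This route does not apply to consumption reported in the daily questionnaires.

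**5. The plan's own sample size.** Inputs from V and IX: control 55%, a 25-point difference (so 30%), 80% power, two-sided alpha 0.05, 10% dropout. Pooled-variance formula, with mean proportion (0.55 + 0.30)/2 = 0.425:

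n = [1.960 × √(2 × 0.425 × 0.575) + 0.842 × √(0.55 × 0.45 + 0.30 × 0.70)]² / 0.25² = 60.2, so 61 per arm.

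Inflated: 61/0.9 = 67.8, so 68 per arm and 136 in total, as stated. The 35% printed beside it does not give 68 (96 per arm, 107 after inflation); that is a separate matter. Either way, the calculation sizes Arm 2 against Arm 1, which is the package contrast, so rewording the aims leaves it untouched.

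**The case against.** The best defence is that the plan already tests the package. The arm label, the Abstract's comparison and hypothesis, the Background and both hypotheses in IX say so. The sentence in IX is also literally true, because the patients who receive education are exactly those in Arm 2. Testing a bundle is legitimate, particularly in a pilot. All of this stands, and it makes the fault an inconsistency in what is claimed rather than a flaw in the comparison. It does not remove the fault: read with Aim 2 and its hypothesis, the IX sentence names education as the cause.

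On Aim 3, the disposal protocol may fairly be read to include the disposal teaching, since its hypothesis speaks of promoting the mechanism as well as providing it. A reader might infer that Aim 3 is a claim about the envelope alone; the text does not say that. What remains is that the general teaching on opioids and pain management comes with the protocol and cannot be separated from it.

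On VIII, a reader might infer that both expected outcomes are component claims. The section opens with expectations for consumption and disposal together, and its second expected outcome is satisfaction with the disposal method, which is descriptive. The criticism there is confined to the sentence on education and consumption.

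A reader might also infer that the envelope lowers actual intake, because tablets that have been mailed cannot be taken. The documents describe it for unused tablets and give no evidence of such an effect. The design cannot exclude it, and the point needs no more than that.

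**Conclusion.** The point holds as a mismatch between the design and some of its stated claims. The randomized comparison identifies the effect of education plus disposal against standard of care on each outcome. It does not identify the effect of education on consumption, nor the effect of the disposal mechanism apart from the education delivered with it. The size of the problem cannot be put as a number: the component effects are unidentifiable at any sample size. A reader might be tempted to say that anything from 0% to 100% of a difference could be due to the envelope, but that range assumes additive effects in the same direction, which the documents do not establish.

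Nor do the documents support the stronger reading that the trial is invalid or must have a third arm. The conclusion rests on two facts in VI: every Arm 2 patient is assigned both components, and Arm 1 is described as receiving neither.

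**What to change.** Restate the following as the effect of the education-plus-disposal package, versus standard of care, on consumption and on disposal:
- Aims 2 and 3 and their hypotheses (III, and the aims repeated in V);
- objectives 2 and 3 in the Abstract;
- the first paragraph of IX;
- the sample size label in V and IX that names only the brochure and video;
- the sentence in VIII on education and consumption.

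Add one sentence to IX saying that no conclusion will be drawn about education or the disposal mechanism alone. Where tablets returned are reported, say that the envelope may raise returns without a change in consumption.

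**Cost.** The total of 136, the data collected and the planned tests do not change; the downside is a narrower conclusion. For comparison only, and assuming that an education-only arm were added and each pairwise contrast had to detect 55% versus 30%, the total would be 3 × 68 = 204 at alpha 0.05, or 3 × 90 = 270 at alpha 0.05/3. Contrasts between components would probably be smaller and need more. The rewording avoids that expense.

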## **I. Abstract**

Opioid medications are widely used after many orthopedic procedures and are routinely prescribed after shoulder replacement surgery. Despite the high prevalence of opioid abuse and misuse, there is no standardized mechanism for patients to dispose of unused opioid medications safely and securely and the average number of opioid pills required after shoulder replacement surgery is still unknown. In a prior pilot study conducted by our group (IRB# 202012142), we analyzed opioid consumption patterns of patients undergoing shoulder arthroplasty as well as their adherence to a safe and secure disposal mechanism for excess opioid pills. We achieved a 94% retention rate and preliminary results showed that most of the subjects were 60 years of age and older.

The objective of the current proposal is to: (1) develop pre-operative education materials related to post-operative opioid use following shoulder arthroplasty; (2) pilot the impact of this educational intervention; (3) examine the effect of providing disposal mechanisms for unused opioid pain medications following shoulder arthroplasty. Our proposal is to conduct a single blinded randomized controlled trial of patients undergoing total shoulder replacement, both anatomic total shoulder arthroplasty (TSA) and reverse shoulder arthroplasty (RSA) at UIHC. This randomized controlled trial will compare: (1) education plus opioid disposal to the standard of care (SC). We hypothesize that pre-operative opioid education modules combined with a structured opioid disposal program will decrease opioid consumption following shoulder arthroplasty.

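### The 80% power is stated for a lower tablet-return rate in Arm 2 (35% against about 55%), whereas Hypothesis 1 expects a higher one

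*Combined protocol and SAP*

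**What the plan says.** Section IX (Data Analysis Plan) gives the direction of the test once. The chi-square test is to determine "whether there is a significantly greater proportion who (Hypothesis 1) return more than 10 tablets in Arm 2 versus Arm 1". The statements of purpose point the same way:

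- The Abstract expects that education plus disposal "will decrease opioid consumption following shoulder arthroplasty".
- Section III, Aim 2, expects that the modules "will prove to be successful in decreasing the amount opioid medication taken after shoulder arthroplasty".
- Section III, Aim 3, expects that "patients undergoing shoulder arthroplasty will more frequently dispose of excess opioid medications".
- Section VIII says "we expect to see a decrease in opioid consumption patterns after shoulder arthroplasty, as well as an increase in disposal of unused opioid pills".

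The sample-size paragraph, printed in both Section V and Section IX, begins "Assuming ~55% will return 10 or more out of 40 tablets in the control group". It then claims 80% power at two-sided 0.05, with 68 per group including 10% dropout, "to detect a 25% difference in the proportion who return 10 or more tabs in the brochure/video intervention group (35", the figure in the bracket being 35%.

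**The concern.** The hypothesis and the power statement describe the same kind of event, tablets returned, and give it opposite signs. Less consumption would leave more tablets available to return, and a better disposal route would bring more of them back. Both mechanisms push Arm 2 above control. An assumed 35% against 55% fits neither, and nothing in the document redefines the 35%, for instance as the share returning fewer than 10.

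This is the only comparison in the plan with a power calculation. As written, the plan states no power for any effect in the direction it hopes to show, so a reader cannot tell what size of benefit 136 patients were meant to detect.

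The cut-off also shifts. Hypothesis 1 counts patients who return more than 10, and the power statement counts those who return 10 or more. A patient who returns exactly 10 is a responder under one rule and not under the other.

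**Working it through.** **Inputs (Sections V and IX; 1:1 allocation from Section VI).** Control rate 0.55. Arm 2 rate 0.35 as printed, or 0.30 from the stated 25-point difference. Two-sided alpha 0.05, power 0.80, 68 per group including 10% dropout, chi-square test.

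**Formulas.** With p̄ the mean of the two rates and d their absolute difference:

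- A = √[2p̄(1−p̄)] and B = √[p1(1−p1) + p2(1−p2)]
- n per group = [(1.960·A + 0.842·B)/d]²; enrolled per group = n/0.9
- Power at n per group = Φ[(d√n − 1.960·A)/B]

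**Step 1: the plan's own figure.**

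- 55% v 35%: A = √0.4950 = 0.7036, B = √0.4750 = 0.6892, d = 0.20. n = 96 and 96/0.9 gives 107 per group. This is not 68.
- 55% v 30%: A = √0.48875 = 0.6991, B = √0.4575 = 0.6764, d = 0.25. n = 61 and 61/0.9 = 67.8, so 68 per group. This matches.

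The printed size therefore fits a 25-point difference, and the 35% conflicts with that difference as well. That is a separate error. Arm 2 lies below control on either reading, so correcting 35% to 30% would leave the direction reversed.

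**Step 2: which way the power points.** Evaluable patients per group are 68 × 0.9 = 61.2, taken as 61. If 55% v 35% were true, power would be Φ[(0.20 × 7.810 − 1.960 × 0.7036)/0.6892] = Φ(0.266) = 60.5%. Almost all of that is for Arm 2 below control. The chance of a significant result in the direction of Hypothesis 1 would be about 0.001%.

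**Step 3: targets in the direction of Hypothesis 1, control held at 55%.**

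| Arm 2 rate | A | B | n per group | Enrolled per group (total) | Power at 61 per group |
|---|---|---|---|---|---|
| 80% (25 points up) | 0.6624 | 0.6384 | 54 | 60 (120) | Φ(1.025) = 84.7% |
| 75% (20 points up) | 0.6745 | 0.6595 | 89 | 99 (198) | Φ(0.364) = 64.2% |

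With continuity correction, 80% needs 62 per group, then 69 (138 in total), and 75% needs 98, then 109 (218 in total). The planned 136 is thus enough, or within two patients of enough, for a 25-point rise, and well short for a 20-point rise.

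**Step 4: transposed arms.** The formulas are symmetric in the two rates, so 30% control v 55% Arm 2 also gives 61, then 68 per group, and 35% control v 55% Arm 2 also gives 60.5% power at 61. The sample size alone cannot show which arm was meant to be higher. The reversal comes from the labels printed beside the rates.

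**The case against.** The best defence is that a sample-size assumption is not a decision rule. The direction of the test is stated once, in Hypothesis 1, and agrees with the Abstract and the aims. The test is two-sided, and the stated 25% difference carries no sign, so the conflict rests on one bracketed figure in a paragraph printed twice. All of this stands, and it limits the point in four places where a reader might infer more.

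- *That a 35% v 55% result would count as success.* It would not. It would match the planning assumption but fail Hypothesis 1 as written.
- *That 35% implies 65% of Arm 2 took more than 30 of 40 tablets, so that education raised consumption.* The endpoint is tablets returned. Unreturned tablets may have been taken, kept at home or disposed of another way, and Aim 3 treats disposal as an effect of its own. The inference needs every unreturned tablet to have been swallowed, which the document does not say.
- *That the reversal leaves the trial too small.* Keeping 25 points and changing only the sign moves power at 61 per group from 80.5% (55% v 30%) to 84.7% (55% v 80%). The figures of 60.5% and 64.2% come from a 20-point difference, not from direction.
- *That Arm 2 must be raised above 55%.* The 55% draws on previous literature and a pilot that studied adherence to a disposal mechanism (Abstract). Section VI says the pilot used the same envelopes now given to Arm 2, and it describes none for Arm 1. Transposed rates, or a control rate set too high, are both open on the text.

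The defence does not remove the contradiction. Both statements use tablets returned, both appear in Section IX, and nothing reconciles them.

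**Conclusion.** The point holds as an internal contradiction in the assumption behind the only powered comparison. Hypothesis 1 expects a greater proportion in Arm 2 and the power statement assumes a smaller one, by 20 points as printed or 25 as described. The stated 80% power is for an effect opposite to the hypothesis. This should be corrected before the results are read.

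The consequence is bounded. A rise can still be detected, and whether 136 patients suffice depends on an upward target that the plan has not stated. The power figures assume a 55% control rate, 61 evaluable per group and a pooled normal approximation without continuity correction. With the correction, at 61 per group, they fall to about 80% for 55% v 80% and about 57% for 55% v 75%. Which rate was misprinted cannot be settled from the document.

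**What to change.** In Sections V and IX:

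1. Restate the two assumed rates so that Arm 2 exceeds control, as Hypothesis 1 requires. Either give an Arm 2 rate above 55%, or correct the control rate if the arms were transposed or if the envelope-based pilot rate does not apply to a control arm without envelopes. Give the reason for each rate.
2. Restate the power that 136 patients, about 61 evaluable per group, provide for those rates, and make the stated difference agree with them.
3. Say that a higher proportion returning tablets is the hypothesised direction, without describing returned tablets as a measure of tablets not consumed.
4. Use one cut-off, 10 or more, in both Hypothesis 1 and the power statement.

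The cost is a protocol and SAP text amendment; the two-sided chi-square test stays as it is. If the sponsor settles on a smaller rise, such as 55% to 75%, it must either accept about 64% power with 136 patients or plan for 198 to reach 80%.

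### Hypothesis 1 and the only power calculation count returned tablets, but only Arm 2 is given the return envelope, so the test can be significant when opioid consumption is equal

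*Combined protocol and SAP*

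**What the plan says.** Aim 2 (section III) is to "Evaluate the impact of educational materials on opioid consumption following shoulder arthroplasty when compared to standard of care". Section IX agrees: "The primary outcome measure is opioid consumption with and without pre-operative opioid education". It adds: "By comparing the two arms we will determine the difference in opioid consumption". A general rule there says that non-normal continuous variables are "compared across intervention groups using Wilcoxon-rank sum tests", with t-tests otherwise.

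The numbered hypotheses in section IX are both chi-square comparisons of proportions. Hypothesis 1 concerns patients who "return more than 10 tablets in Arm 2 versus Arm 1". Hypothesis 2 concerns proper disposal of unused tablets. The sample-size paragraph, printed in sections V and IX, also uses a return proportion. Its control rate rests on previous literature and "data from our pilot study that showed nearly 55% of subjects returned 10 or more out of 40 tablets".

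Section VI gives Arm 2 a brochure, a video that covers disposal, and a prepaid envelope run by an outside waste-disposal company, the same envelope as in the pilot. Arm 1 receives standard care, which includes no preoperative teaching on opioid use or disposal; no return route is described for it. Participants in general are told that "they will have to answer daily questionnaires about pain management and opioid consumption", by text message for two weeks. Non-responders and continuing users can catch up at the 2-week or 6-week visit.

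**The concern.** The primary outcome and the tested variable are different things. Consumption has no numbered hypothesis, endpoint definition, analysis window or stated power; section VI fixes only when survey data are collected. The plan does not assign Hypothesis 1 to an aim. Since Hypothesis 2 matches Aim 3, Hypothesis 1 is the only numbered hypothesis that could serve Aim 2.

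'Return' is not defined, and the plan does not say how returned tablets are counted. On its plain meaning, a tablet must be both left over and handed back to count. The intervention supplies the means of handing back, and raising disposal is one of its stated purposes (Aim 3 and section VIII). Unequal return behaviour is therefore what the trial expects. A significant Hypothesis 1 would be a valid finding about returns, but it would not show lower opioid use and would largely repeat Hypothesis 2. The risk is that it is reported as the answer to Aim 2 and carried into the larger study that section VIII foresees.

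The assumed 55% control rate has a related weakness. It is a return rate from a pilot that used these envelopes. The documents do not say that the 55% was measured through them, but they give no basis for expecting 55% in an arm without them.

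**Working it through.** **1. The plan's own figure.** Inputs from sections V and IX: control rate 0.55, two-sided alpha 0.05, 80% power, 10% dropout, 68 per group. Pooled-variance formula:

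n = [1.960·√(2·p̄(1−p̄)) + 0.842·√(p₁(1−p₁) + p₂(1−p₂))]² / (p₁−p₂)²

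With 0.55 and 0.30 (p̄ = 0.425): (1.960 × 0.699 + 0.842 × 0.676)² / 0.25² = 3.76 / 0.0625 = 60.2, so 61 per group, and 61 / 0.9 = 67.8, so 68. The stated size is reproduced, which confirms that the quantity powered is a return proportion.

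**2. Model for equal consumption.** Let L be the share of patients left with enough tablets, the same in both arms because consumption is equal. Let r₁ and r₂ be the probabilities that such a patient hands them back. Hypothesis 1 then compares L·r₁ with L·r₂. Any excess of r₂ over r₁ favours Arm 2 whatever the value of L. The direction needs no numerical assumption; the size does.

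**3. Size.** Assumptions: 61 evaluable per arm, Arm 2 returning 55%, Arm 1 returning 0.55 × r. The rejection rate of the uncorrected two-sided chi-square test was obtained by summing the binomial probabilities of all 62 × 62 possible outcomes that are significant. The 0.025 column is the first step of a step-down Bonferroni procedure for two hypotheses.

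| r (Arm 1 relative to Arm 2) | Arm 1 rate | Rejects at 0.05 | Rejects at 0.025 |
|---|---|---|---|
| 1.0 | 55% | 5.6% | 2.3% |
| 0.9 | 49.5% | 10.3% | 5.0% |
| 0.8 | 44% | 25% | 15% |
| 0.7 | 38.5% | 47% | 33% |
| 0.5 | 27.5% | 88.5% | 81% |

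At r = 0.9, 9.7 of the 10.3 points favour Arm 2; at lower r nearly all do.

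Hand check at r = 0.7: the null standard error is √(2 × 0.4675 × 0.5325 / 61) = 0.0903 and the alternative one is √((0.2475 + 0.2368) / 61) = 0.0891. Φ[(0.165 − 1.960 × 0.0903) / 0.0891] = Φ(−0.135) ≈ 0.45, close to the exact 0.47.

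Setting the uptakes separately at L = 55% tells the same story. Uptake of 20% against 50% (rates 11% and 27.5%) rejects in 65% of trials, and 30% against 50% (16.5% and 27.5%) in 32%.

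**4. The alternative test.** Trials were simulated with 40 tablets dispensed to everyone, identical consumption in both arms, 61 per arm, three assumed consumption distributions and the five values of r (10,000 trials per cell). The Wilcoxon test on tablets consumed rejected in 4.6% to 5.4% of trials in all 15 cells. The chi-square test on returns rose from about 6% at r = 1.0 to 88–89% at r = 0.5. This assumes accurate self-report.

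**5. What 136 patients give for consumption.** With 61 evaluable per arm and two-sided alpha 0.05, a t-test has 80% power for a standardised difference of 0.51. For the Wilcoxon test this is 0.511 / √0.955 = 0.52. With an assumed SD of 8 to 15 tablets, that is about 4 (0.51 × 8) to 8 (0.52 × 15) tablets. Power is 59% at 0.4 and 38% at 0.3.

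**The case against.** The strongest reply is that 'return' may mean 'left over'. Hypothesis 1 is listed apart from proper disposal, a threshold out of 40 tablets looks like a proxy for consumption, and 55% in an arm without envelopes fits leftover tablets better than mailed ones. On that reading, with equal dispensed quantities, the access bias largely disappears. This stands as a possibility, but the evidence is only suggestive. Section IX says returned, the design is built around a mail-in envelope, and the direction does not settle it: the power paragraph has fewer returns in Arm 2 (35%), while Hypothesis 1 expects more. Dispensed quantity is also not listed as collected. An undefined variable in the only powered test needs repair on either reading.

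Second, the plan already promises a comparison of consumption, its Wilcoxon or t-test rule could cover it, and nothing calls Hypothesis 1 the primary test. That is correct, so consumption is not left wholly unanalysed. But the comparison has no defined endpoint, window or stated power, while the comparison that has both a numbered hypothesis and a sample size measures something else.

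Third, the uptake ratios are assumed, and the lack of a return route in Arm 1 is inferred from the arm descriptions in the text available. Both limits stand. They affect the size of the bias more than its direction.

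Fourth, the study is partly a pilot. It still expects to show reduced consumption, so the attribution matters.

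**Conclusion.** The concern holds and should be fixed before analysis. The plan's primary outcome is consumption, but its only powered test counts returns, and the intervention supplies the route for returning. On the plain reading of 'return', and with equal consumption, a modest shortfall in Arm 1 returns (80% of the Arm 2 rate) makes the test significant in about a quarter of trials, and a halved rate in 88.5%. These sizes rest on 61 evaluable patients per arm and on assumed uptakes. The direction rests only on Arm 2 patients being more likely to hand tablets back. If 'return' is shown to mean self-reported leftovers in both arms, the bias largely goes. The undefined term, and the missing endpoint, window and power for consumption, remain.

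**What to change.** 1. **Make Hypothesis 1 a test of consumption.** Possible wording: *Hypothesis 1 (Aim 2, primary): total opioid tablets taken from surgery to [one named existing visit], self-reported by REDCap or clinic survey, is lower in Arm 2 than in Arm 1 (Wilcoxon rank-sum, two-sided).* Ask the item identically of everyone in both arms, whether or not tablets were returned. Use dispensed minus consumed as a measure of unused tablets only if dispensed quantity is recorded for all participants.
2. **Keep returned or disposed tablets for Aim 3 (Hypothesis 2) only.** Define 'return' and say how it is counted in each arm.
3. **Restate the sample-size paragraph for the consumption endpoint.** Use a control value that does not depend on envelope returns and a direction that agrees with Aim 2, and state the power that 136 patients give. If a proportion is kept, use one cut-off (the plan has both more than 10 and 10 or more). For orientation, 61 evaluable per arm gives 64% power for 55% against 75% (80% needs 89 evaluable, 99 enrolled per arm) and 85% for 55% against 80% (54 evaluable, 60 enrolled).

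A separate point can be settled in the same paragraph: the stated 25% difference and the printed 35% disagree. 68 per group matches 55% against 30%, whereas 55% against 35% has about 63% power with 61 evaluable per arm.

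The cost is rewording, a recalculated paragraph, and one consumption item at an existing visit, with the clinic survey extended from non-responders and continuing users to everyone. No extra visit is needed. There are two drawbacks: self-report may itself differ by arm because only Arm 2 is educated, and 136 patients may be too few for a standardised difference below about 0.5.
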